- c. **Consent process:** There is no difference in the consent process for the treatment or control groups. Evaluation consent is a condition of eligibility for the study, so no individual is randomized to a condition until after informed consent is obtained. As incentive to participate, a \$40 gift card is given to individuals who enroll in the study each time they complete a questionnaire (baseline, 3-month, and 9-month), and a \$5 gift card is given to individuals each time they respond to a request by study staff to update their contact information.⁶

After the individual has been screened and found eligible to participate in the study, the study coordinator goes through the *Participant Informed Consent Form* with her. This provides the individual with information about the study, outlines why she has been invited to participate, and addresses any questions that may arise. This process involves a paragraph-by-paragraph exploration of the consent form by the study coordinator and the female and constant “checking in” with the individual to be sure she fully understands the study requirements. At the end of this exercise, she is asked to provide consent if she wishes to participate in the study.

- d. **Data collection:** Data used for investigating both primary and secondary research questions are obtained from the *Participant Questionnaire* administered at baseline, three months post-baseline, and nine months post-baseline. The questionnaire is used to collect data on study participants’ self-reported contraceptive use and knowledge, sexual behavior and experiences, and intentions, thoughts, and feelings related to sexual behaviors. It is administered three times at the following time points:
- a. Baseline – at the enrollment session just prior to the participant receiving their assigned intervention
 - b. Three months post-baseline – three months after the baseline questionnaire administration
 - c. Nine months post-baseline – nine months after the baseline questionnaire administration

While we collect data at three times over nine months, our analysis of primary and secondary research questions is concerned only with data gathered at baseline and three months post-

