⁶ At the beginning of March 2017, the IRB approved a request to increase the gift card incentive offered to participants living in one region for completion of the baseline questionnaire from \$40 to \$60. This was done due to the higher cost of living in the region relative to the other study regions, and because the \$40 incentive amount seemed insufficient to attract participants to the study. In April 2017, the IRB also approved a request to increase the gift card incentive offered to participants who did not complete their follow-up questionnaires within two months of the follow-up window opening from \$40 to \$60. This was done to increase the likelihood of capturing data from harder-to-reach participants.

baseline.⁷ Exploratory research questions will investigate mediating factors, subgroup effects, outcomes at nine months, and other, exploratory outcomes. Study participants who are offered *Plan A* and *The Toxic Life Cycle of a Cigarette* videos receive the same questionnaire. The questionnaire contains 75 items and takes, on average, 18 minutes to complete. The instrument was constructed by PRG staff and is composed of items and scales that have been used in previous research on sexual behaviors and contraceptive use. The instrument was reviewed by health professionals and pilot-tested by young women with similar characteristics to our proposed study population. The questionnaire includes the same items at each time point and will measure the same constructs with identical measures at each administration.

There are no differences in data collection procedures for treatment and control groups. Data collection is conducted identically for both groups.

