$Base_{participant\ T}$ - the number of participants randomly assigned to the control group

$Received_{participant\ T}$ - the number of participants randomly assigned to the control group who received the *Plan A* video

Levels of crossover and contamination will be reported in the findings section of our final impact report.

- f. **Analytic approach for primary research questions:** As detailed in our primary research questions, this study investigates whether offering *Plan A* to participants impacts their reported LARC use, number of times having sex without condoms, and STI testing. We do this within the intent to treat (ITT) framework, which does not measure the effect of the participant’s exposure to the treatment itself but rather the effect of the offer of the treatment relative to the offer of receiving the control condition. This framework maintains the integrity of the experimental structure by including all participants who were randomized (except those who attrite) in the analytic sample, thereby maintaining an exogenous assignment of participants to experimental condition. Bias can be insinuated, however, through self-selection if any participant who is randomized fails to provide outcome data.
- i. **Model specification and covariates:** The primary research questions under investigation in this study are whether offering *Plan A* to participants impacts their: (1) reported use of LARC, (2) times having sex without condoms, and (3) reported STI testing partners (see Table 1 in Appendix A for variable constructions). We propose to estimate these impacts using a regression that will model intervention effects as a function of assignment to *Plan A* (i.e., Treatment), relevant baseline covariates, a baseline measure of the outcome variable, and regional (blocking) indicators (see Table 2 in Appendix A for variable constructions).³⁹ Although a straight difference-of-means approach should provide unbiased estimates of the

³⁸ In the OAH Impact Analysis Plan guidance for Cohort 2 Tier 2B grantees, contamination is described as occurring “when individuals assigned to the counterfactual condition end up receiving all or portions of the conditions intended only as part of the intervention.” Given this, we calculate contamination in our sample as participants assigned to the control condition who received any amount of the *Plan A* video, as this is the intended treatment condition.

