³⁹ With the assumption that we maintain low attrition and differential attrition and that the study otherwise executes the RCT with integrity, we should be able to estimate an un-biased estimate of the average treatment effect of the intent to treat participants with *Plan A* by comparing differences in the means of the outcome variable reported by the treatment group with those reported by the control group. We could then provide a compelling response to our research question by testing the hypothesis that there is no difference between the two groups using straight-forward hypothesis testing statistics (t-test). With that said, we propose a regression-based model that includes covariates, because randomization should ensure covariates are uncorrelated with the treatment variable (i.e., they should not affect the estimate of the treatment effect), and in the instance they are significant predictors of the outcome, their inclusion in a regression model will decrease the standard error of the estimates, making them more precise. See: Angrist, J. D., & Pischke, J. (2009). *Mostly harmless econometrics: An empiricist's companion*. Princeton: Princeton University Press; Rosenblum, M. and van der Laan, M. J. (2009), Using Regression Models to Analyze Randomized Trials: Asymptotically Valid Hypothesis Tests Despite Incorrectly Specified Models. *Biometrics*, 65: 937-945. doi:10.1111/j.1541-0420.2008.01177.x.

effect of the treatment, we propose a model-based approach because it will increase the precision of those estimates. The empirical model will be estimated with an OLS regression (using Stata).⁴⁰ We present the empirical model here:

$$Y_{Post} = \beta_0 + \beta_1 T + \beta_2 Y_{Pre} + \sum (\beta_p X_p) + \varepsilon$$

Where:

Y_{Post} – The outcome variable of interest, either: 1) times having sex without condoms in the past 3 months (continuous; values range 0 to k , where 0= has had sex without condoms 0 times in past 3 months, and k = number of times having sex without condoms in past 3 months); 2) current LARC use (0= not currently using a LARC; 1= currently using a LARC); or 3) STI testing in the past 3 months (0=not tested for STIs/STDs in past 3 months; 1= tested for STIs/STDs in past 3 months) reported by participant i at the 3-month follow-up. (see Table 1 for full details on the variable construction).

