Y_{Pre} – The baseline measure of the outcome variable of interest reported by participant i at baseline (see Table 2 for full details on the variable construction); variable will be re-centered at the grand mean for analysis.

T – A dummy treatment indicator variable whose value equals 1 if the participant is randomized into the treatment group and zero otherwise.

X – A p vector of baseline (i.e., measured prior to receiving intervention or exogenous to treatment) participant-level covariates as well as blocking variables to account for the variation in outcomes associated with these groups. These covariates, listed in detail in Table 2 in Appendix A, will include:

- a) Age – self-reported age (based on date of birth) at screening (continuous; range 18-19); variable will be re-centered at the grand mean for analysis.
- b) Race – self-reported as Black/African American at screening (0 = identify as another race/do not identify race; 1 = identify as Black/African American); each of the variables will be re-centered at the grand mean for analysis.
- c) Ethnicity – self-reported as Hispanic, Latino, or of Spanish origin at screening (0=do not identify as Hispanic/Latino/Spanish origin; 1=identify as Hispanic, Latino, of Spanish origin); variable will be re-centered at the grand mean for analysis.
- d) High school education – self-reported education at baseline. A dummy variable (0= has not completed high school; 1= has completed high school); variable will be re-centered at the grand mean for analysis.
- e) Region – An $n-1$ vector of region indicator dummy variables that are coded one if the intervention was delivered at region n and coded zero otherwise. Region 1 is the reference category and is excluded from analysis. The dummy variables will be mean-centered for analysis to facilitate interpretation.⁴¹

β_0 – The intercept term, which represents, depending on the outcome measure of interest in the analysis, the outcome for the average control participant with all other variables in the model held constant at their mean.

β_1 – This is the parameter estimate of substantive interest. β_1 represents, depending on the outcome measure of interest in the analysis, either: 1) the adjusted mean difference in

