- g. **Analytic approach for secondary research questions:** We intend to use the same analytic approach as described above to address all secondary research questions, with the exception of our method related to multiple comparisons. Following guidance provided under the grant for our impact analysis plan,⁴⁴ we will not adjust for multiple comparisons in our secondary outcome analyses, regardless of outcome domains.

5) Additional planned analyses

We intend to investigate the following research questions in addition to the primary and secondary research questions described above.

Antecedents of Sexual Behavior

- a. What are the short-term (three-month follow-up) and long-term (nine-month follow-up) impacts of the offer to participate in *Plan A* (treatment) relative to the offer to participate in *The Toxic Life Cycle of a Cigarette* (comparison) on participants' reported perception of risk and severity for pregnancy and HIV/STIs after the end of treatment?
- b. What are the short-term (three-month follow-up) and long-term (nine-month follow-up) impacts of the offer to participate in *Plan A* (treatment) relative to the offer to participate in *The Toxic Life Cycle of a Cigarette* (comparison) on participants' reported intention to use LARC after the end of treatment?
- c. What are the short-term (three-month follow-up) and long-term (nine-month follow-up) impacts of the offer to participate in *Plan A* (treatment) relative to the offer to participate in *The Toxic Life Cycle of a Cigarette* (comparison) on participants' reported intention to use other effective contraception methods (including condoms) after the end of treatment?
- d. What are the short-term (three-month follow-up) and long-term (nine-month follow-up) impacts of the offer to participate in *Plan A* (treatment) relative to the offer to participate in *The Toxic Life Cycle of a Cigarette* (comparison) on participants' reported self-efficacy to communicate with health care providers after the end of treatment?
- e. What are the short-term (three-month follow-up) and long-term (nine-month follow-up) impacts of the offer to participate in *Plan A* (treatment) relative to the offer to participate in *The Toxic Life Cycle of a Cigarette* (comparison) on participants' reported self-efficacy to negotiate condom use after the end of treatment?

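### The primary LARC model omits baseline intention to use LARC, which appears to be collected before the video, so some precision of unknown size is forgone

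*SAP*

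**What the plan says.** Section 4f.i defines the benchmark regression as treatment plus "relevant baseline covariates, a baseline measure of the outcome variable, and regional (blocking) indicators". The baseline term is "The baseline measure of the outcome variable of interest reported by participant i at baseline", so the LARC model carries baseline LARC use. The remaining terms are introduced with "These covariates, listed in detail in Table 2 in Appendix A, will include" and are age, Black/African American, Hispanic/Latino, high-school completion and region. Table 2 adds no intention or other psychosocial measure.

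Footnote 39 gives the reason for adjusting: where covariates predict the outcome, "their inclusion in a regression model will decrease the standard error of the estimates".

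On what is collected, section 3d says the questionnaire covers "intentions, thoughts, and feelings related to sexual behaviors" and that "The questionnaire includes the same items at each time point and will measure the same constructs with identical measures at each administration". The baseline administration comes just before the assigned video. Section 5 names "reported intention to use LARC after the end of treatment" as an exploratory outcome at three and nine months, and lists the same construct as a potential mediator of current LARC use. The SAP gives no reason for leaving its baseline value out of the primary model.

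**The concern.** By the plan's own precision argument, the LARC covariate set is weak where it is most needed. Among women not using LARC at baseline, the baseline outcome is a constant and explains none of the variation in uptake. The other terms are also restricted by eligibility. Age covers only 18 to 19, and every participant must identify as African American, Latina or both, so a woman coded 0 on one indicator should be coded 1 on the other.

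Intention to use LARC is an obvious candidate for separating later adopters from the rest, and the plan's mediation question already supposes that intention is linked to use. If the item is on the baseline questionnaire, using it needs no new data. At stake is the width of the interval for one of three primary outcomes.

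**Working it through.** **The plan's own figure.** The SAP gives no precision figure for LARC. The nearest is the minimum detectable effect size (MDES) of 0.12 at 1,770, in the study changes timeline. It names no outcome, power, covariate R² or attrition. With two-sided 5% (section 4f.i), 1:1 allocation (section 3b) and an assumed 80% power, no covariates and no attrition:

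MDES = (1.960 + 0.842) × √(4/1770) = 0.133.

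Reaching 0.12 would need R² = 1 − (0.12/0.133)² ≈ 0.19. The stated figure can therefore be neither confirmed nor called wrong.

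**Is the item available and usable?** Section 3d says intentions are measured and that the items are identical at each administration. Section 5 says LARC intention is a study measure. Together these imply a baseline value, although the item itself is not reproduced. Random assignment comes just before the baseline questionnaire, but the coordinator is trained to keep the assignment from the participant (section 3b), and the video follows the questionnaire. Baseline intention thus has the same standing as the baseline outcome already in the model.

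**Gain in precision.** All rates below are assumptions. Let L be baseline LARC use, c continuation, f the share of non-users intending LARC, u1 and u0 uptake in intenders and others, and u = f·u1 + (1−f)·u0. The treatment effect is ignored, and the demographic terms are taken to add nothing.

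- Residual variance given baseline LARC: V1 = L·c(1−c) + (1−L)·u(1−u)
- Given intention as well: V2 = L·c(1−c) + (1−L)·[f·u1(1−u1) + (1−f)·u0(1−u0)]
- Fall in variance = 1 − V2/V1; fall in SE = 1 − √(V2/V1)

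Central case (L = 0.15, c = 0.90, f = 0.25, u1 = 0.30, u0 = 0.06):

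- u = 0.075 + 0.045 = 0.12
- V1 = 0.0135 + 0.85 × 0.1056 = 0.10326
- V2 = 0.0135 + 0.85 × (0.0525 + 0.0423) = 0.09408
- Variance falls 8.9%; SE falls 1 − √0.911 = 4.5%
- Non-users supply 0.08976/0.10326 = 87% of V1

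Low and high ends over L = 0.10-0.20 and f = 0.20-0.30, with c = 0.90. Here V1 − V2 = (1−L)·f(1−f)·(u1−u0)².

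| Case | L | f | u1 v u0 | V1 | V1 − V2 | Variance falls | SE falls |
|---|---|---|---|---|---|---|---|
| Low | 0.20 | 0.20 | 15% v 8% | 0.0861 | 0.0006 | 0.7% | 0.4% |
| Central | 0.15 | 0.25 | 30% v 6% | 0.1033 | 0.0092 | 8.9% | 4.5% |
| High | 0.10 | 0.30 | 40% v 5% | 0.1269 | 0.0232 | 18.2% | 9.6% |

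**What baseline LARC already explains.** In the central case follow-up LARC use is 0.15 × 0.90 + 0.85 × 0.12 = 0.237, and its variance is 0.237 × 0.763 = 0.1808. Baseline LARC explains 1 − 0.1033/0.1808 = 43%, and intention adds 0.0092/0.1808 = 5 points. Over the whole grid baseline LARC explains about 28% to 55%. The MDES at 1,770 is then 0.133 × √(1 − R²): 0.101 centrally, with a range of 0.090 to 0.113.

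**The case against.** The strongest reply is that nothing here is an error. The model is prespecified, it adjusts for the baseline outcome and the blocking factor, and it has a no-covariate check. Footnote 39 says predictive covariates reduce the standard error. It does not promise to include every predictor, and choosing among 75 questionnaire items is a matter of judgement. That stands, and it limits the point to a missed gain. It is also true that the intention item's wording, scale and handling of current LARC users are not shown, and that the intending share and the uptake gap are assumed.

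Two stronger readings are tempting, and the documents do not support either.

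- **That the cut to 1,770 leaves the LARC model short of an MDES of 0.12.** On the same assumed rates, baseline LARC use alone brings the MDES at full enrolment to 0.090-0.113, below 0.12. With an assumed 20% attrition (1,416 analysed) the central value is about 0.112. Only the least favourable corner, with R² near 0.28, passes 0.12, at about 0.126. The documents state no power, R² or attrition from which to establish a shortfall.
- **That each primary model should also carry the baseline values of the other two primary outcomes.** Nothing in the SAP shows that they predict across outcomes, and there is a hazard. Section 4c.iv sets both baseline and follow-up sexual-behaviour values to missing when they disagree over time, so baseline missingness can depend on follow-up answers. In the LARC and STI-testing models, a step 5 missing-data indicator for baseline condomless sex could then carry post-randomisation information.

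**Conclusion.** The point holds as a modest efficiency gain left unused in the primary LARC model. The treatment estimate is not biased by the omission, and the SAP does not contradict itself here.

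Under the stated assumptions residual variance falls by 0.7% to 18.2%, and the standard error by about 0.4% to 10%, with 8.9% and 4.5% in the central case. The low end is negligible. Any correlation between intention and the demographic terms would change these figures. The conclusion also rests on the inference that the intention item is on the baseline questionnaire. Because the change costs almost nothing and follows the plan's own rationale, it is worth making, but it is not urgent.

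**What to change.** Before outcomes are analysed, add baseline intention to use LARC to the covariate list in section 4f.i and as a row in Table 2, for the LARC model only and alongside baseline LARC use.

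- Confirm that the item is on the baseline questionnaire, and state its coding.
- Handle current LARC users through the baseline LARC term, for example by setting intention to its reference value for them. The two terms then separate current users, intending non-users and other non-users.
- Treat missing intention items by the step 5 dummy-variable adjustment. Intention is not used to build a primary or secondary outcome, so the over-time consistency recoding should not reach it.
- Keep sensitivity analysis 1 (no covariates) as the check.
- Leave the other two primary models as they are.

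The cost is one line in 4f.i, one table row, and one or a few degrees of freedom, including any missing-data indicator. No new data are needed and no cases are lost.
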